#### 4.5 Adjustment for Multiplicity

Since all analyses are exploratory in nature, no adjustments will be made for multiplicity in any statistical analyses performed.

#### 4.6 Software for Analyses

Statistical analyses will be performed using SAS version 9.4 or higher or R v3.3.1 or higher. All tables, listings and figures presented in the analysis will be created using either SAS v9.4 or Rv3.3.1 or higher.

#### 5.0 DATA SUMMARIES

#### 5.1 Accrual and Participant Characteristics

Demographic data collected include baseline age, sex, race and ethnicity. Demographic data will be listed by participant and will include study registration date and information on study eye.

#### 5.2 Medical and Ophthalmic History

A listing of history of medical and ophthalmic conditions as well as any physical examination findings at baseline will be provided.

#### 5.3 Analysis of Protocol Compliance

Listings of participant-specific and non-participant-specific protocol deviations and unanticipated problems will be presented.

#### Study Procedure Deviations

This table will present the number of procedures not completed, the expected number of procedures completed, and the percentage of procedures missed for each individual participant and collectively for all participants, cumulatively throughout the study (Table 1). Number of procedures not completed is defined when the site reports a missed procedure or when the protocl monitors note missed procedures at a site, and will be presented as a sum. Expected number of procedures completed is defined based on the study flowsheet included in the protocol, and will also be presented as a sum. Percentage of procedures missed will be calculated as follows:

(N procedures not completed / N expected procedures completed)\*100

The table will flag occurrences where collectively or individually, participants missed more than 15% of the expected procedures if the number of expected procedures is > 16. Otherwise, if the number of expected procedures is 16 or less, the table will flag occurrences where collectively or individually, participants missed two or more procedures.

### Visit Schedule Deviations

This table will present the number of expected visits, number of missed study visits, the percentage of missed study visits, the number of out of window visits, and the percentage of out of window visits for each individual participant and collectively for all participants, cumulatively throughout the study (Table 2). Number of expected, missed and out of window study visits will be calculated from the study flowsheet and will all be presented as sums. The percentage of missed study visits will be calculated as:

## (N visits missed / N expected visits)\*100

Similarly, the percentage of out of window study visits will be calculated as:

(N visits out of window / N expected visits) 
$$*100$$

If the number of expected visits is > 16, then the table will flag occurrences where collectively or individually participants missed more than 15% of the expected visits; similarly, the table will flag occurrences where collectively or individually participants completed more than 15% of the expected visits outside of the window.

Otherwise, if the number of expected visits is 16 or less, then the table will flag occurrences where collectively or individually participants mised or completed out of window two or more visits.

#### 6.0 **TREATMENT**

Information related to injections administered at each visit will be listed.

## 7.0 **PRIMARY OUTCOMES ANALYSIS**

The analysis of primary outcome will be considered exploratory; no formal statistical analysis will be performed.

All treatment-emergent ocular and systemic AEs reported through Week 52 will be summarized. Treatment-emergent AEs are those events occurring at the time of or after administration of first dose of study drug. Frequency and percentage of participants, total number of AEs and number of AEs experienced by each participant will be summarized by seriousness, severity of the AE, relatedness to the study treatment and Medical Dictionary for Regulatory Activities (MedDRA) System Organ Class (SOC); tabulations will also be provided by timing of occurrence of AEs (while on treatment vs. after discontinuaion of treatment) (Tables 3 and 4).

#### 8.0 SECONDARY OUTCOMES ANALYSIS

The analysis of secondary outcomes will be considered exploratory. Therefore, no formal statistical analysis will be performed. In addition to the data summaries detailed below, exploratory plots showing values over time for relevant measurements may be presented.

#### 8.1 Adverse Events (AEs)

All ocular and systemic AEs reported through Week 104 will be tabulated similar to the primary outcome (Tables 5 and 6).

#### 8.2 Retinal Capillary Hemangioma(s) (RCH)

The following will be assessed as secondary outcomes at Weeks 52 and 104 compared to baseline; information will also be presented for each participant separately (Table 7).

- Frequency and percentage of participants with reduction in size of at least one RCH, in the absence of other ablative treatment assessed by fundus photography and FA;
- Frequency and percentage of participants with increase, decrease, mixed effects and no change in size of RCH measured by fundus photography and FA;
- Frequency and percentage of participants with increase, decrease, mixed effects and no change in exudation measured by fundus photography, OCT and FA;
- Frequency and percentage of participants with increase, decrease, mixed effects and no change in epiretinal proliferation, fibrosis or retinal traction assessed by OCT and fundus photography;
- Frequency and percentage of participants undergoing ablative treatment of RCH or ocular surgery;
- Frequency and percentage of participants with successful ablative treatment of RCH;
- Frequency and percentage of participants with appearance of one or more new RCH.

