3.1.2 Exclusion Criteria

 Participant has a history or evidence of significant cardiac disease (for example, use of cardiac medications aside from agents to control blood pressure, past acute coronary syndrome, past myocardial infarction, past revascularization procedure or arrhythmias requiring past or present treatment).

- 2. Participant has a history of stroke or transient ischemic attack. Note: cerebrovascular manifestations and/or complications of central nervous system hemangioblastomas are not exclusionary, in the absence of past stroke or transient ischemic attack.
- Participant has used systemic medication with significant anti-VEGF or anti-PDGF activity within 30 days of study entry or expects use of such a medication within 12 months of study entry.
- 4. Participant is medically unable to comply with study procedures or follow-up in the judgment of the investigator.
- 5. Participant has a diagnosis of diabetic mellitus (type 1 or type 2). Any one of the following will be considered sufficient evidence that diabetes is present:
 - Current regular use of insulin for the treatment of diabetes,
 - Current regular use of oral anti-hyperglycemia agents for the treatment of diabetes,
 - Hemoglobin A1C of \geq 6.5%, or
 - Documented diabetes by ADA and/or WHO criteria.

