4.6.7 Concomitant Medications or Treatments

Any potential participant likely to need systemic treatment with an agent having significant anti-VEGF or anti-PDGF activity within 12 months of enrollment should not be entered in the study (see Section 3.2.2, Exclusion Criteria). However, once participants are enrolled in the study, concomitant therapies for non-ocular conditions are allowed without restriction. In the event that a participant requires systemic treatment with either anti-VEGF therapy or anti-PDGF therapy, interruption or discontinuation of combination investigational treatment will be considered and discussed with other treating physicians.

Standard care therapies for VHL disease, including laser photocoagulation, cryotherapy, photodynamic therapy, surgery, ocular radiation and any medication use associated with these treatments (such as use of systemic corticosteroids to minimize exudation from RCH undergoing ablative treatment) will be considered for significant clinical worsening at any time during the study, for clinical improvement at any time starting at Week 16 (as in a case where clinical improvement makes an eye more amenable to ablative or surgical treatment), and without restriction starting at Week 40 (in anticipation of unavailability of investigational product after Week 48).

Significant clinical worsening is defined as ANY OF THE FOLLOWING, assessed by clinical evaluation and /or clinical imaging with OCT, FA and fundus photography, as applicable, IF assessed to represent progression of ocular VHL disease in the judgment of the investigator:

- 1. A decrease in BCVA of \geq 15 letters; OR
- 2. An increase in exudation, epiretinal proliferation or hemorrhage threatening vision in the judgment of the investigator; OR
- 3. New or more extensive retinal detachment; OR
- 4. Increase in size of RCH; OR
- 5. Appearance of new RCH.

Clinical improvement is defined as ANY OF THE FOLLOWING, assessed by clinical evaluation and /or clinical imaging with OCT, FA and fundus photography, as applicable, IF associated with a significant improvement in chance of treatment success or significant reduction in treatment risk with standard of care therapies in the judgment of the investigator:

- 1. A decrease in exudation, epiretinal proliferation or hemorrhage; OR
- 2. Resolution or reduction of retinal detachment; OR
- 3. Decrease in size of RCH; OR
- 4. Disappearance of RCH.

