8.2 Secondary Outcomes

Secondary outcomes will include tabulation of AEs reported through Week 104 and the following measures in the study eye at Week 52 and 104: the proportion of participants experiencing reduction in size of at least one RCH in the absence of other ablative treatment (assessed by fundus photography and FA); the proportion of participants experiencing moderate vision loss (defined as a loss of \geq 15 letters from baseline on EVA testing); mean change in visual acuity; change in size of RCH (measured by fundus photography and FA); change in epiretinal proliferation, fibrosis or retinal traction (assessed by OCT and fundus photography); proportion of participants undergoing ablative treatment of RCH or ocular surgery; proportion of participants with successful ablative treatment of RCH; and the proportion of participants with appearance of one or more new RCH.

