17.0 ALTERNATIVES TO PARTICIPATION

Standard care for RCH in VHL ocular disease includes ablative therapies such as laser photocoagulation and trans-scleral cryotherapy. Other therapies include verteporfin photodynamic therapy, episcleral brachytherapy and external beam radiotherapy. Vitreoretinal surgery is used as an adjunct to ablative therapy in order to address vision-threatening epiretinal proliferation, tractional or rhegmatogenous retinal detachment or vitreous hemorrhage.

Participants may receive standard care treatment for RCH (laser photocoagulation and cryotherapy) and complications of RCH (vitreoretinal surgery) when indicated for significant clinical worsening during this study. If a participant achieves clinical improvement during the study that allows for standard care treatment that was not previously feasible, this treatment may be administered anytime starting at the Week 16 visit.

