Concomitant therapies for non-ocular conditions are allowed without restriction. If systemic treatment with either anti-VEGF or anti-PDGF therapy is required, interruption or discontinuation of combination investigational treatment will be considered and discussed with other treating physicians. Any participant who discontinue study treatment will be asked to return for all future study visits.

Standard care therapies for VHL disease, including laser photocoagulation, cryotherapy, photodynamic therapy, surgery, ocular radiation and any medication use associated with these treatments (such as use of systemic corticosteroids to minimize exudation from RCH undergoing ablative treatment) will be considered for significant clinical worsening at any time during the study, for clinical improvement at any time starting at Week 16 (as in a case where clinical improvement makes an eye more amenable to ablative or surgical treatment), and without restriction starting at Week 40 (in anticipation of unavailability of investigational product after Week 48).

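### The RCH responder outcome excludes only other ablative treatment, so shrinkage after starting a systemic anti-VEGF or anti-PDGF drug, which is permitted after enrolment, is scored as a response

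*SAP*

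**What the plan says.** Protocol 8.2 defines the outcome as the proportion of participants with "reduction in size of at least one RCH in the absence of other ablative treatment". SAP 8.2 analyses it as "reduction in size of at least one RCH, in the absence of other ablative treatment", and Protocol 9.2, SAP 3.5.2 and the first row of SAP Table 7 carry the same single condition. Table 7 records Yes or No for each participant at Weeks 52 and 104. Neither document defines ablative treatment.

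On systemic drugs, Protocol 3.1.2 excludes anyone who has used a systemic agent with significant anti-VEGF or anti-PDGF activity within 30 days of entry, or who "expects use of such a medication within 12 months of study entry". After entry the position changes. Protocol 4.6.7 says that "once participants are enrolled in the study, concomitant therapies for non-ocular conditions are allowed without restriction". SAP 3.1 adds: "If systemic treatment with either anti-VEGF or anti-PDGF therapy is required, interruption or discontinuation of combination investigational treatment will be considered". Nothing is said about how such a participant is scored.

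On local treatment, Protocol 4.6.7 permits "Standard care therapies for VHL disease, including laser photocoagulation, cryotherapy, photodynamic therapy, surgery, ocular radiation" for significant worsening at any time, for improvement from Week 16, and "without restriction starting at Week 40".

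**The concern.** The condition on ablative treatment is there so that a Yes reflects the study injections and not something else done to the lesion. Table 7 already has an unconditional row for change in RCH size, so the first row earns its place only if its condition works.

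The condition covers local destruction of the lesion but not a systemic drug acting on VEGF or PDGF, the targets of the two study drugs. The protocol's rationale (1.5 and 1.7) is that combined VEGF and PDGF blockade may make RCH regress. A systemic agent with those actions would, if that rationale is right, produce the same finding as the one under test. The trial has one uncontrolled arm, so nothing in the design would separate the two explanations.

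The scenario is not remote from this population. Protocol 3.1.1 lists renal cell carcinoma among the lesions that establish VHL disease, and Protocol 1.3 cites anti-VEGF antibody treatment in advanced clear cell renal carcinoma.

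**Working it through.** The plan gives no power, error rate or derived sample size for this outcome, so there is no figure to reproduce. The check is mainly one of following the rules as written.

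**Following one participant through the rules**

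1. At entry no systemic anti-VEGF or anti-PDGF treatment is expected, so the participant is eligible (Protocol 3.1.2).
2. After enrolment such treatment becomes necessary. It is permitted, and stopping the study injections is only considered (Protocol 4.6.7, SAP 3.1).
3. The participant stays in the analysis population whether or not study treatment stops (SAP 4.2).
4. At Week 52 or 104 one RCH is smaller than at baseline, and no ablative treatment has been given.
5. Both parts of the definition are met, so the first row of Table 7 reads Yes.

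**Timing**

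- The 12-month horizon of the entry criterion ends at about Week 52. It concerns expectation at entry, so it does not prevent unforeseen use in the first year either.
- The second assessment is 104 − 52 = 52 weeks beyond that horizon.
- The last study injection is at Week 48, so the Week 104 assessment is 104 − 48 = 56 weeks after it.

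**Size**

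With N = 3 (SAP 4.1), one reclassified participant changes the proportion by 1/3 = 33.3 percentage points. For example, with exact (Clopper-Pearson) 95% limits:

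| Responders | Proportion | 95% limits |
|---|---|---|
| 1 of 3 | 33.3% | 0.8% to 90.6% |
| 0 of 3 | 0% | 0% to 70.8% |

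The documents give no rate for such drug use. Let q be the chance that a participant starts such a drug and then shows a reduction. The chance of at least one such case among three is 1 − (1 − q)³:

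| q (assumed) | Chance of at least one |
|---|---|
| 5% | 1 − 0.95³ = 14.3% |
| 10% | 1 − 0.90³ = 27.1% |
| 20% | 1 − 0.80³ = 48.8% |

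These values of q only show a range; none is an estimate.

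**Is ablative treatment wide enough to cover photodynamic therapy and radiation?**

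- Protocol 1.2 discusses laser, cryotherapy, brachytherapy, external beam radiotherapy and photodynamic therapy in one paragraph on choosing ablative treatment. It sets vitreoretinal surgery apart as an adjunct.
- Protocol 4.6.7 lists photodynamic therapy and ocular radiation alongside laser and cryotherapy.
- Protocol 17.0 gives laser and cryotherapy as examples of ablative therapies, then continues: "Other therapies include verteporfin photodynamic therapy, episcleral brachytherapy and external beam radiotherapy".

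The first two places favour the wider meaning. The third leaves some doubt, because the term is never defined.

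**The case against.** The best case against the point is that it matters little here. The outcome is secondary and all analyses are exploratory, with no formal testing (SAP 4.0 and 8.0). The sample size statement disclaims any definitive finding on efficacy, and no decision rule uses this proportion. Table 7 shows each participant separately, and concomitant medications are assessed at every visit (Protocol Appendix 2), so an attentive reader could pick out a confounded case among three. A shift of 33.3 points is what any single reclassification does when N = 3. All of this stands and limits the weight of the point. None of it supplies a scoring rule, and the rule as written returns the wrong answer for such a participant.

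A second objection is that the documents do not show that systemic agents shrink RCH. Protocol 1.3 reports that no VEGF antagonist given intravitreally has produced regression. That evidence is confined to intravitreal use and to VEGF blockade alone, so it does not settle what a systemic or dual-target agent would do. Still, a reader should not infer that such misattribution is likely: the documents support only that the definition allows it.

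A reader might also infer from Protocol 17.0 that photodynamic therapy and radiation fall outside ablative treatment, so that shrinkage after either would also count as a response. The documents do not support that. The list of ablative therapies there is given by example, the section describes alternatives to participation and defines no outcome, and Protocol 1.2 and 4.6.7 point the other way. What remains is an undefined term.

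**Conclusion.** The gap for systemic drugs follows from the text. The condition names only ablative treatment, systemic anti-VEGF or anti-PDGF drugs are permitted after enrolment, they are not ablative, and the participant remains in the analysis. A reduction after starting one is scored Yes. This is a misattribution built into the definition, and the Week 104 assessment is the more exposed to it.

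Each affected participant moves the reported proportion by 33.3 points. Whether anyone is affected depends on two things the documents do not quantify: how often such drugs are started, and whether they shrink RCH. Given the descriptive purpose and the per-participant display, this is a modest improvement to scoring, worth making because it is cheap. For photodynamic therapy and radiation, only a one-line definition is needed.

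**What to change.** 1. In Protocol 8.2 and 9.2, SAP 3.5.2 and 8.2, and the first row of Table 7, extend the condition to: *in the absence, before the assessment, of other ablative treatment or systemic anti-VEGF or anti-PDGF treatment*. Apply it separately at Week 52 and Week 104.
2. In that row, replace Yes/No by three categories: *Yes*; *reduction, other treatment given*; *No*. Keep all participants in the denominator, as SAP 4.3 provides. The unconditional row for change in RCH size stays as it is.
3. As a minor clarification, state that ablative treatment includes photodynamic therapy and ocular radiation, consistent with Protocol 1.2 and 4.6.7. Use that definition both in the first row and in the row for participants undergoing ablative treatment or ocular surgery.

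The cost is a change of wording and one extra category in Table 7. The concomitant medication record already holds the data needed on systemic drugs. The responder count may be slightly less favourable. A participant who responded by Week 52 and later started a systemic agent would no longer be a plain Yes at Week 104, though the Week 52 entry would still show the response. Only scoring changes; what participants may receive does not.

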#### 8.3 Electronic Visual Acuity (EVA)

Binocular visual acuity measures and visual acuity measures for each eye will be obtained using an EVA algorithm. EVA with manifest refraction will be performed if a change in EVA  $\geq$  10 E-ETDRS letters ( $\geq$  0.20 logMAR) since previous visit is observed.

Summary statistics for change in total letters read at Weeks 52 and 104 compared to baseline will be presented. Frequency and percentage of participants with moderate vision loss at Weeks 52 and 104, defined as loss of  $\geq$  15 letters from baseline, will also be summarized (Table 8). Values from assessments performed with manifest refraction will be used for the analysis if available; otherwise, values from assessments performed without manifest refraction will be used.

#### 9.0 SAFETY ANALYSIS

In addition to the data summaries detailed below, exploratory plots showing values over time for relevant measurements may be presented.

#### 9.1 Natural Progressions of the Disease

All natural progressions of the disease reported through Week 104 will be listed.

#### 9.2 **Post-Injection Evaluation**

Intraocular pressure (IOP) in the injected eye is measured by Tono-Pen within 20 minutes after injection. Post-injection IOP and change from pre-injection measurement will be summarized for each visit (Table 10). Frequency and percentage of participants with the following will be presented for each visit:

- > 24 mmHg IOP after injection in the treated eye (Table 10);
- Severe pain, absence of hand-motion vision or absence of perfusion of the retinal arterioles following an injection (Table 9);
- Intraocular inflammation as assessed by the presence of anterior chamber or vitreous cell on ophthalmoscopy by grade (Table 9); and
- Any other complications following an injection (Table 9).

#### 9.3 Intraocular Pressure (IOP)

Summary statistics of baseline and change from baseline in IOP at each visit will be presented (Table 10). If study treatment is administered at a visit, then the pre-injection value will be used in the summaries. Post-injection values are summarized as described in Section 9.2.

#### 9.4 EVA

Summary statistics of baseline and change from baseline in total letters read at each visit will be presented (Table 11).

#### 9.5 Other Ophthalmologic Assessments

All ophthalmologic data collected will be descriptively summarized. If appropriate, exploratory plots may be presented.

If sufficient data are available, frequency and percentage of participants who meet the definition of clinical improvement and time to clinical improvement will also be summarized; otherwise, the data will be listed.

